8. STUDY POPULATION

Pediatric patients (age < 18 years) with a documented diagnosis of PNH will be enrolled and treated with ALXN1210 at approximately 10 investigative sites globally. Approximately 13 patients will be enrolled to ensure at least 10 evaluable patients complete the 26-week period.

Individuals who do not meet the criteria for participation in this study (screen failure) may be rescreened once.

Prospective approval of protocol deviations to recruitment and enrollment criteria, also known as protocol waivers or exemptions, is not permitted.

8.1. Inclusion Criteria

Patients are eligible for enrollment in the study only if they meet all of the following criteria and none of the exclusion criteria:

- 1. Male and female patients < 18 years of age and weighing ≥ 5 kg at the time of consent.
- 2. Documented diagnosis of PNH, confirmed by high-sensitivity flow cytometry evaluation (Borowitz, 2010) of red blood cells (RBCs) and white blood cells (WBCs), with granulocyte or monocyte clone size of \geq 5%.
- 3. For patients not currently treated with eculizumab, presence of 1 or more of the following PNH-related signs or symptoms within 3 months of Screening: fatigue, hemoglobinuria, abdominal pain, shortness of breath (dyspnea), anemia, history of a major adverse vascular event (including thrombosis), dysphagia, or erectile dysfunction; or history of packed red blood cell (pRBC) transfusion due to PNH.
- 4. Lactate dehydrogenase (LDH) values at Screening as follows:
 - a. For patients not currently treated with eculizumab, LDH level $\geq 1.5 \times \text{ULN}$.
 - b. For patients who are currently taking eculizumab, LDH $\leq 1.5 \times$ ULN (sample must be obtained on a scheduled eculizumab-dosing day prior to dose administration [ie, at trough eculizumab level] and analyzed by the central laboratory).
- 5. To reduce the risk of meningococcal infection (*N meningitidis*), all patients must be vaccinated against meningococcal infections within 3 years prior to, or at the time of, initiating study drug. Patients who initiate study drug treatment less than 2 weeks after receiving a meningococcal vaccine must receive treatment with appropriate prophylactic antibiotics until 2 weeks after vaccination. Patients who cannot be vaccinated must receive antibiotic prophylaxis for the entire treatment period and for 8 months following last dose.
- 6. Patients must have been vaccinated against *Haemophilus influenzae* type b (Hib) and *Streptococcus pneumoniae* according to national and local vaccination schedule guidelines, as appropriate.
- 7. Female patients of childbearing potential (ie, have achieved menarche) and male patients with female partners of childbearing potential must follow protocol-specified guidance for avoiding pregnancy while on treatment and for 8 months after last dose of study drug.

8. Patient's legal guardian must be willing and able to give written informed consent and the patient must be willing to give written informed assent (if applicable as determined by the central or local Institutional Review Board [IRB]/Institutional (or Independent) Ethics Committee [IEC]) and comply with the study visit schedule.

8.2. Exclusion Criteria

Patients will be excluded from study enrollment if they meet any of the following criteria:

- 1. Platelet count $< 30,000/\text{mm}^3 (30 \times 10^9/\text{L})$ at Screening.
- 2. Absolute neutrophil count $< 500/\mu L$ (0.5 × 10⁹/L) at Screening.
- 3. History of bone marrow transplantation.
- 4. History of *N meningitidis* infection.
- 5. History of unexplained, recurrent infection.
- 6. Active systemic bacterial, viral, or fungal infection within 14 days prior to study drug administration on Day 1.
- 7. History of malignancy within 5 years of Screening with the exception of adequately treated nonmelanoma skin cancer or carcinoma in situ of the cervix.
- 8. History of or ongoing major cardiac, pulmonary, renal, endocrine, or hepatic disease (eg, active hepatitis) that, in the opinion of the Investigator or Sponsor, precludes the patient's participation in an investigational clinical trial.
- 9. Unstable medical conditions (eg, myocardial ischemia, active gastrointestinal bleed, severe congestive heart failure, anticipated need for major surgery within 6 months of Screening, coexisting chronic anemia unrelated to PNH) that would make them unlikely to tolerate the requirements of the protocol.
- 10. Concomitant use of anticoagulants is prohibited if not on a stable regimen for at least 2 weeks prior to Day 1.
- 11. History of hypersensitivity to any ingredient contained in the study drug, including hypersensitivity to murine proteins.
- 12. Females who plan to become pregnant or are currently pregnant or breastfeeding.
- 13. Females of childbearing potential who have a positive pregnancy test result at Screening or on Day 1.
- 14. Participation in another interventional treatment study or use of any experimental therapy within 30 days before initiation of study drug on Day 1 in this study or within 5 half-lives of that investigational product, whichever is greater.
- 15. Known or suspected history of drug or alcohol abuse or dependence within 1 year prior to the start of Screening.
- 16. Known medical or psychological condition(s) or risk factor that, in the opinion of the Investigator or Sponsor, might interfere with the patient's full participation in the study,

pose any additional risk for the patient, or confound the assessment of the patient or outcome of the study.

8.3. Discontinuation

8.3.1. Withdrawal of Patients

A patient has the right to withdraw from the study at any time. If a patient discontinues from the study, an Early Termination (ET) visit (as shown in the Schedule of Assessments, Section 7.3) will be performed, and the Sponsor and site monitor should be notified as soon as possible. In addition, a Follow-up Phone Call will be performed 8 weeks (\pm 5 days) following the patient's last dose of study drug to collect concomitant medications, procedures, and adverse events. Patients who withdraw from the study will not be replaced.

Patients should be permanently discontinued from ALXN1210 treatment if any of the following occur during the study:

- Serious infusion reaction (such as bronchospasm with wheezing or requiring ventilator support or symptomatic hypotension, refer to Appendix B) or serum sickness-like reactions manifesting 1 to 14 days after drug administration;
- Severe uncontrolled infection;
- Pregnancy or planned pregnancy; or
- If the Alexion Medical Monitor or the Investigator deems it to be in the best interest of the patient.

The Investigator should speak with the Medical Monitor prior to discontinuing a patient's study treatment. If a patient is discontinued from study drug, the patient should be encouraged to return for the remainder of his or her scheduled protocol visits until starting a different complement-targeted therapy.

The reason for the treatment or study discontinuation will be recorded on the eCRF.

If a patient is discontinued from the study with an ongoing AE or an unresolved laboratory result that, in the opinion of the Investigator, is significantly outside of the reference range and clinically significant (Section 11.4), the Investigator will attempt to provide follow-up until a satisfactory clinical resolution of the laboratory result or AE is achieved.

If a female patient is permanently discontinued from ALXN1210 treatment due to pregnancy, the Investigator will attempt to follow-up until the outcome of the pregnancy (see Section 11.8).

8.3.2. Discontinuation of Study/Site Termination by Sponsor or Health Authority

The Sponsor or health authority may terminate the study for reasonable cause. Conditions that may warrant termination of the study include, but are not limited to:

- Discovery of an unexpected, serious, or unacceptable risk to patients enrolled in the study
- Sponsor decision to suspend or discontinue testing, evaluation, or development of the study drug

- Failure of the Investigator to comply with the approved protocol, pertinent guidelines, and/or regulations
- Submission of knowingly false information from the Investigator to the Sponsor and/or health authorities

Should the study be terminated early, the Sponsor will notify the health authority and IRB/IEC according to local requirements.

8.4. End of Study Definition

The end of the study is defined as the date of the last patient's last visit or follow-up (whether on site or via phone call) in the Extension Period.

9. STUDY TREATMENT

9.1. Materials and Supplies

9.1.1. Description of Study Drugs

ALXN1210 is a humanized, anti-C5 mAb produced in Chinese hamster cells. It was designed through minimal targeted engineering of eculizumab by introducing 4 unique amino acid substitutions to its heavy chain to extend antibody half-life. ALXN1210 and eculizumab share over 99% primary amino acid sequence identity and have very similar pharmacology.

ALXN1210 drug product is supplied for clinical studies as a sterile, preservative-free 10-mg/mL solution in single-use vials and is designed for infusion by diluting into commercially available saline (0.9% sodium chloride injection; country-specific pharmacopeia) for administration via IV infusion (Table 4).

Refer to the current ALXN1210 IB for additional information.

Table 4: Study Drug

Product Name	ALXN1210
Dosage Form	Concentrated solution (10 mg/mL) for infusion
Route of Administration	Intravenous infusion
Physical Description	Clear to translucent, slight whitish color, practically free from particles
Manufacturer	Alexion Pharmaceuticals, Inc. or Contracted Manufacturing Organization

9.1.2. Study Drug Packaging and Labeling

ALXN1210 is packaged in US Pharmacopeia/European Pharmacopeia Type 1 borosilicate glass vials and stoppered with a butyl rubber stopper with an aluminum overseal and a flip-off cap. Study drug will be supplied in kits. Please refer to the Pharmacy Manual for details.

Study drug orders will be released to each site upon receipt of all required documents based upon applicable regulations.

9.1.3. Study Drug Storage

Upon arrival of the study drug kits at the study site, the pharmacist or designee should promptly remove the study drug kits from the shipping cooler and store them in their original cartons under refrigerated conditions at 2°C to 8°C (35°F to 47°F) and protected from light. ALXN1210 should not be frozen. Study drug must be stored in a secure, limited-access storage area, and the temperature must be monitored daily.

The admixed drug product should be at room temperature prior to administration. The material must **not** be heated (eg, by using a microwave or other heat source) other than by ambient air temperature.

Please consult the Pharmacy Manual for further information regarding the storage conditions of reconstituted ALXN1210.

9.1.4. Study Drug Preparation and Infusion

ALXN1210 must NOT be administered as an IV push or bolus injection. Infusions of study drug must be prepared using aseptic technique. The patient's required dose of ALXN1210 will be further diluted into commercially available saline (0.9% sodium chloride; country-specific pharmacopeia) at the volume specified in Table 5. ALXN1210 admixture will be administered to the patient using an IV tubing administration set via an infusion pump. Use of a 0.2 micron filter is required during infusion of ALXN1210.

Table 5:	Dosing Reference Chart for ALXN1210 Dose Preparation
----------	---

Dose Type	Body Weight (kg) ^a	Dose (mg)	ALXN1210 Volume (mL)	Saline Volume (mL)	Total Volume (mL)	Minimum Infusion Duration minutes (hours)	Maximum Infusion Rate (mL/hour)
Loading	\geq 5 to < 10	600	60	60	120	228 (3.8)	31.5
	$\geq 10 \text{ to} < 20$	600	60	60	120	113 (1.9)	63.1
	\geq 20 to < 30	900	90	90	180	86 (1.5)	120.0
	\geq 30 to < 40	1200	120	120	240	77 (1.3)	184.6
	\geq 40 to < 60	2400	240	240	480	114 (1.9)	253
	\geq 60 to < 100	2700	270	270	540	102 (1.7)	318
	≥ 100	3000	300	300	600	108 (1.8)	333
Maintenance	\geq 5 to < 10	300	30	30	60	113 (1.9)	31.5
	$\geq 10 \text{ to} < 20$	600	60	60	120	113 (1.9)	63.1
	\geq 20 to < 30	2100	210	210	420	194 (3.3)	127.2
	\geq 30 to < 40	2700	270	270	540	167 (2.8)	192.8
	\geq 40 to < 60	3000	300	300	600	140 (2.4)	250
	\geq 60 to < 100	3300	330	330	660	120 (2.0)	330
	≥ 100	3600	360	360	720	132 (2.2)	328

Note: Please refer to the Pharmacy Manual for additional dose preparation instructions.

Doses of study drug must only be prepared and dispensed by qualified study personnel. Study drug is to be dispensed only to enrolled patients who are confirmed eligible for participation in this study. Once study drug is prepared for a patient, it can only be administered to that patient. Vials of study drug are for one-time use only and any drug product remaining in the vial should not be used for another patient. Any drug remaining in the infusion tubing or infusion bag should not be used for another patient.

Further details on preparation and dose administration of study drug, as well as disposal of study drug, can be found in the Pharmacy Manual.

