14.2. Determination of Sample Size

This study is descriptive in nature and not statistically powered for hypothesis testing due to the rarity of disease in pediatric patients. Approximately 13 patients will be enrolled to ensure at least 10 evaluable patients complete the 26-week period, which is expected to be sufficient to adequately describe PK/PD in pediatric patients with PNH.

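### In Protocol Table 5 the minimum infusion minutes do not match the printed hours or maximum rates in several weight bands below 60 kg (by up to 4.7%)

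*Protocol*

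**What the plan says.** Table 5 in Protocol section 9.1.4 is the dose preparation chart. It has 14 rows: seven weight bands for the loading dose and the same seven for maintenance. Three of its columns matter here:

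- the volume to be infused, headed "Total Volume (mL";
- a lower limit on time, headed "Minimum Infusion Duration minutes (hours", with minutes first and hours in parentheses in the same cell;
- an upper limit on rate, headed "Maximum Infusion Rate (mL/hour".

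The section requires an infusion pump and sends sites to the Pharmacy Manual for further preparation and administration detail. That manual is not among the documents. Section 9.1.4 does not say how the durations or rates were derived, how they were rounded, or which figure governs if they differ. Protocol Table 6 and SAP Table 2 repeat the doses but give no durations or rates.

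**The concern.** The three columns are linked by arithmetic: volume divided by the shortest permitted time is the fastest permitted rate. If the printed minutes and the printed rate describe the same limit, that quotient should equal the printed maximum, apart from rounding. In several paediatric rows it is higher. In three of those rows the single duration cell also gives two different minimum times, one in minutes and one in hours.

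The consequence is practical. A pump set by volume over the printed minutes runs above the printed maximum rate in those rows, while a pump set by the printed rate does not. Whether an infusion is within the table can therefore depend on the column that was read. The patients are children, Appendix B provides for infusion reactions, and section 9.10 allows some infusions to be given remotely or at home, so the chart should carry one consistent set of figures.

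**Working it through.** **Inputs.** All come from Protocol Table 5: total volume V (mL), minimum minutes m, hours h in parentheses, and maximum rate R (mL/h).

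**Formulas.** Rate from hours = V / h. Rate from minutes = V / m × 60. Excess = (rate from minutes / R) − 1.

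| Dose | Band (kg) | V | m | h | R | V/h | V/m × 60 | Excess |
|---|---|---|---|---|---|---|---|---|
| Loading | 5 to < 10 | 120 | 228 | 3.8 | 31.5 | 31.6 | 31.6 | +0.3% |
| Loading | 10 to < 20 | 120 | 113 | 1.9 | 63.1 | 63.2 | 63.7 | +1.0% |
| Loading | 20 to < 30 | 180 | 86 | 1.5 | 120.0 | 120.0 | 125.6 | **+4.7%** |
| Loading | 30 to < 40 | 240 | 77 | 1.3 | 184.6 | 184.6 | 187.0 | +1.3% |
| Loading | 40 to < 60 | 480 | 114 | 1.9 | 253 | 252.6 | 252.6 | −0.1% |
| Loading | 60 to < 100 | 540 | 102 | 1.7 | 318 | 317.6 | 317.6 | −0.1% |
| Loading | ≥ 100 | 600 | 108 | 1.8 | 333 | 333.3 | 333.3 | +0.1% |
| Maintenance | 5 to < 10 | 60 | 113 | 1.9 | 31.5 | 31.6 | 31.9 | +1.1% |
| Maintenance | 10 to < 20 | 120 | 113 | 1.9 | 63.1 | 63.2 | 63.7 | +1.0% |
| Maintenance | 20 to < 30 | 420 | 194 | 3.3 | 127.2 | 127.3 | 129.9 | **+2.1%** |
| Maintenance | 30 to < 40 | 540 | 167 | 2.8 | 192.8 | 192.9 | 194.0 | +0.6% |
| Maintenance | 40 to < 60 | 600 | 140 | 2.4 | 250 | 250.0 | 257.1 | **+2.9%** |
| Maintenance | 60 to < 100 | 660 | 120 | 2.0 | 330 | 330.0 | 330.0 | 0.0% |
| Maintenance | ≥ 100 | 720 | 132 | 2.2 | 328 | 327.3 | 327.3 | −0.2% |

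**1. Reproducing the printed rates.** V / h returns all 14 printed maximum rates to within 0.3%. The rates appear to have been calculated from the hours, not the minutes.

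**2. Minutes against rates.** To allow for rounding, add 0.5 min to each duration and allow half a unit in the last printed digit of R. Eight rows still exceed R: loading 10 to < 20, 20 to < 30 and 30 to < 40 kg, and maintenance in all five bands below 60 kg. The closest of these is maintenance 30 to < 40 kg: 540 / 167.5 × 60 = 193.4 against 192.8. Loading 5 to < 10 kg does not survive the allowance: 120 / 228.5 × 60 = 31.5.

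**3. Minutes against hours.** In the three largest rows the two figures in the cell do not agree under ordinary rounding:

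- loading 20 to < 30 kg: 86 / 60 = 1.43 h, printed 1.5 h (1.5 × 60 = 90 min);
- maintenance 40 to < 60 kg: 140 / 60 = 2.33 h, printed 2.4 h (2.4 × 60 = 144 min);
- maintenance 20 to < 30 kg: 194 / 60 = 3.23 h, printed 3.3 h (3.3 × 60 = 198 min).

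In the other five rows the hours do match the minutes at one decimal (113 / 60 = 1.88, 77 / 60 = 1.28, 167 / 60 = 2.78). There the gap arises only because the rate follows the rounded hours. In all 14 rows the printed hours equal the minutes rounded up to the next 0.1 h.

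**4. Can both limits be met?** The time needed at the printed maximum rate is V / R × 60. For the three largest rows it is 180 / 120.0 × 60 = 90.0 min (printed 86), 600 / 250 × 60 = 144.0 min (printed 140) and 420 / 127.2 × 60 = 198.1 min (printed 194). For the five smaller rows it is 1.0 to 1.3 min above the printed minutes. The worst shortfall in any row is maintenance ≥ 100 kg: 720 / 328 × 60 = 131.7 min against 132, or 0.3 min. An infusion at or below R therefore meets the minutes everywhere, to within about 0.3 min.

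**5. A case that falls between the figures.** A loading infusion of 88 min at 20 to < 30 kg meets the 86 minutes, falls short of the 1.5 hours, and runs at 180 / 88 × 60 = 122.7 mL/h against a maximum of 120.0.

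**The case against.** The strongest reply is that the table can be followed as printed. A minimum time and a maximum rate both push towards slower infusion, so one can be tighter than the other without conflict. The rates follow from the hours, and the hours fit rounding up. A site would have to use exactly the minimum minutes and disregard both the hours in the same cell and the rate in the next column. The largest gap is about 4 minutes, and the Pharmacy Manual may settle the matter.

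Most of this stands, and it rules out stronger readings that a reader might infer:

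- *That the two limits contradict each other and staff cannot satisfy both.* Step 4 shows that they can.
- *That these are breached safety limits.* The documents never give the figures that label.
- *That using the minutes would be a reportable deviation.* SAP section 7.1.2 leaves important deviations to a procedure that is not among the documents.
- *That a rate differing between loading and maintenance at one weight (120.0 against 127.2 mL/h at 20 to < 30 kg) is itself an error.* Nothing says a band must have one rate, and the two differ in every band from 20 kg upward.

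The reply does not remove the mismatch. The rounding rule is inferred, not stated, and three cells still print two different minimum times. A pointer to another manual does not make the protocol's own table consistent.

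**Conclusion.** The inconsistency is real but minor. In 8 of 14 rows, all below 60 kg, an infusion over exactly the printed minimum minutes runs above the printed maximum rate: by 4.7%, 2.9% and 2.1% (about 4 minutes each) in three rows, and by 0.6 to 1.3% (about 1 minute) in five. In the three larger rows the minutes and hours in one cell also disagree, and the table does not say which governs.

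This rests on the printed figures alone and on treating the minutes, the hours and the rate as expressions of one limit. Rounding up of the hours is the likely origin, but the documents do not confirm it. The Pharmacy Manual could not be checked. Which value is clinically right is not judged here.

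No effect on the analysis is shown. Compliance in SAP section 7.3.1 counts infusions, not rates, and SAP section 7.2.1 bases the PK calculations on actual dosing and sampling times.

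**What to change.** Reconcile the minutes, hours and mL/h in every row of Table 5, so that volume divided by the minimum time does not exceed the maximum rate, whichever time unit is read. State the rounding rule in a table note and say which column governs. Check the Pharmacy Manual, and the home health care manual if it repeats the figures, against the reconciled table. The choice of values belongs to the sponsor.

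The cost is a table correction and a site notification. The SAP needs no change.

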9.1.5. Study Drug Handling and Disposal

All clinical study material provided to the Investigator will be stored in a secure place, and allocated and dispensed by appropriately trained persons. Detailed records of the amounts of the investigational product received, dispensed, and destroyed will be maintained.

^a Body weight is obtained at the study visit. If the study drug needs to be prepared the night prior to the visit, the weight from the previous visit may be used.

Unless otherwise notified, empty vials and vials with residual materials should be kept for inspection and accountability by the study monitor prior to their destruction or handled per local pharmacy standard operating procedures for clinical study drugs.

To satisfy regulatory requirements regarding drug accountability, at the end of the study all remaining ALXN1210 inventory will be reconciled and destroyed or returned to Alexion or designee according to applicable regulations.

Please refer to the Pharmacy Manual for further information.

9.2. Treatments Administered

Patients will receive a loading dose of ALXN1210 on Day 1, followed by maintenance dosing of ALXN1210 on Day 15 and q8w thereafter for patients weighing \geq 20 kg, or q4w for patients weighing \leq 20 kg, as shown in Table 6. With the agreement of the Alexion Medical Monitor, the 600 mg loading dose may be given to patients weighing \geq 5 to \leq 10 kg as 2 separate infusions administered no more than 24 hours apart. Dosages are based on the patient's body weight recorded on the day of dosing or the most recently recorded weight. For patients entering the study on eculizumab therapy, Day 1 of study treatment will occur 2 weeks from the patient's last dose of eculizumab.

Table 6:	Loading and Maintenance Treatment Regimen	IS

Body Weight Range (kg) ^a	Loading Dose (mg)	Maintenance Doses (mg)	Maintenance Dosing Frequency
\geq 5 to < 10	600 ^b	300	q4w
$\geq 10 \text{ to} < 20$	600	600	q4w
\geq 20 to < 30	900	2100	q8w
\geq 30 to < 40	1200	2700	q8w
\geq 40 to < 60	2400	3000	q8w
\geq 60 to < 100	2700	3300	q8w
≥ 100	3000	3600	q8w

Abbreviations: q4w = once every 4 weeks; q8w = once every 8 weeks

With the agreement of the Alexion Medical Monitor, administration of a supplemental dose of ALXN1210 is permitted.

After the Primary Evaluation Period, all patients will roll over into an Extension Period and continue their weight-based maintenance dose of ALXN1210 on Day 183 and q8w thereafter for patients weighing ≥ 20 kg, or q4w for patients weighing ≤ 20 kg, until the product is registered or approved (in accordance with country specific regulation) or for up to 4 years, whichever occurs first, except in Norway where the Extension Period will be 4 years.

The actual time of all dose administrations, including any supplemental dose or dose administered as 2 separate infusions as noted above, will be recorded on the patient's eCRF.

^a Dose regimen will be based on body weight obtained at the study visit. If the study drug needs to be prepared the night prior to the visit, the weight from the previous visit may be used.

b With the agreement of the Alexion Medical Monitor, the 600 mg loading may be given to patients weighing ≥ 5 to < 10 kg as 2 separate infusions administered no more than 24 hours apart.

